6.11 Adverse Events, Device Observations, & Complications

Reportable events and device observations, as defined below, will be recorded in the subject’s medical record and on the appropriate forms.

6.11.1 Serious Adverse Event (SAE)

A serious adverse event is an untoward medical occurrence where the outcome is:

- Death;

³ Cook et al. *Neurology*. 2013 Mar 12; 80(11 Suppl 3): S49–S53.

- Life-threatening event (places the subject at immediate risk of death from the experience as it occurred);
- Hospitalization (initial or prolonged) if admission to hospital was warranted as a result of an adverse event;
- Disability or permanent damage (substantial disruption of one's ability to carry out normal life functions);
- Congenital anomaly or birth defect;
- Required intervention to prevent permanent impairment or damage;
- or
- Important medical event that required medical or interventional treatment to prevent one of the previous outcomes.

Investigators will record SAEs on the AE log and report to Tactile Medical and IRB (as required) within 10 working days of becoming aware of the event.

6.11.2 Device-Related Adverse Event (AE)

A device-related AE is defined as any untoward medical occurrence in a subject that is associated with the use of the Flexitouch Plus device.

All device-related AEs will be recorded on the AE log. Complaint reporting will be reported through standard commercial means.

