6.11.4 Venous-, Lymphedema-, and Lipedema-Related Complications

Information about venous-, lymphedema-, and lipedema-related complications, including cellulitis, lymphangitis, deep vein thrombosis, skin breakdown, lymphorrhea, and lymphangiosarcoma, will be recorded on the Complication & Healthcare Utilization log.

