8.0 Risk Analysis and Adverse Events

Study subjects will be informed of any significant new findings that develop during the course of this study that may affect their willingness to continue participation. The investigator will oversee all safety aspects of the study, report all adverse events to the IRB, and ensure each subject is treated identically. Should a subject choose to terminate his or her participation in the study, he or she will be treated according to the standard of care that applies at the point of withdrawal.

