8.1 Treatment Risks

Participants enrolled in this study are not expected to be at any higher or additional risk than those who use conservative care (compression garments), since IPC pressures do not exceed the pressures of static compression garments. IPC and static compression are minimal risk therapies with nominal complications or adverse events.

Likely:

- Local skin irritation
- Pain or discomfort
- Increased swelling

Less Likely:

- Cellulitis
- New or increased edema in the trunk and/or genital region

Highly Unlikely:

- Electric shock (if Flexitouch Plus device is not maintained or used properly)

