11.1 Data Safety Monitoring

The Investigator will be responsible for the monitoring of study data and subject safety. Due to the small number of research subjects, the most comprehensive and effective method of monitoring will be an individual case review by the Investigator (or designee). The Investigator will be made aware of all serious and device-related adverse events; therefore, the responsibility for reporting adverse events is shared with the Investigator and research team.

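### Non-serious events reach the AE log only if tied to Flexitouch Plus, so overall non-serious AE rates cannot be compared between the arms

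*Combined protocol and SAP*

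**What the plan says.** Section 6.11 opens by limiting what is recorded: "Reportable events and device observations, as defined below, will be recorded in the subject’s medical record and on the appropriate forms". The categories that follow are these.

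- Serious events (6.11.1), with no restriction by arm or device: "Investigators will record SAEs on the AE log and report to Tactile Medical and IRB (as required) within 10 working days".
- Non-serious events (6.11.2), restricted to the device: "A device-related AE is defined as any untoward medical occurrence in a subject that is associated with the use of the Flexitouch Plus device". The section continues: "All device-related AEs will be recorded on the AE log".
- Disease-related complications (6.11.4), on a separate log with no restriction by arm, device or seriousness: "lipedema-related complications, including cellulitis, lymphangitis, deep vein thrombosis, skin breakdown, lymphorrhea, and lymphangiosarcoma, will be recorded on the Complication & Healthcare Utilization log".
- Device observations (6.11.5), which concern Flexitouch Plus. The same section sends unexpected side effects of graduated compression to the manufacturer or MedWatch and names no study log for them.

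Table 1 schedules an adverse event, complication and device observation assessment at Baseline and Follow-up without separating the arms.

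Three other sections describe the scope of adverse event handling. Section 8.0 has the investigator "report all adverse events to the IRB, and ensure each subject is treated identically". Section 8.3 qualifies IRB reporting by what is required. Section 11.1 says: "The Investigator will be made aware of all serious and device-related adverse events". On comparative risk, section 8.1 states: "Participants enrolled in this study are not expected to be at any higher or additional risk than those who use conservative care".

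**The concern.** Whether a non-serious event enters the AE log depends on a link to a device that only one arm uses during the treatment period. The same skin irritation would be logged in a Flexitouch Plus user if tied to the device, and would have no place on the log in a control subject wearing a compression garment. A difference between the arms on that log could then reflect the recording rule and not the treatment.

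The gap falls on common events. Section 8.1 discusses pneumatic and static compression together and lists skin irritation, pain or discomfort, and increased swelling as likely. If the sponsor later wants to describe how the two regimens were tolerated, or to say that the data agree with the 8.1 expectation, the AE log will not support it. Events that were never written down may not be recoverable.

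**Working it through.** The plan states no figure on this point, so there is nothing to reproduce. The check takes the event types in 8.1 and asks where each would be recorded for a control subject during the treatment period.

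1. Local skin irritation (likely). It has no AE-log route under 6.11.2. Section 6.11.4 names skin breakdown, which is a more severe event. No questionnaire asks about skin irritation. The physical exam in 6.8 notes clinical symptoms at two visits but does not name it.
2. Pain or discomfort (likely). It has no AE-log route. Pain is rated at both visits, but each instrument has its own window: the NRS asks about the present moment (Appendix E), PROMIS Pain Interference covers 7 days (Appendix C), and the RAND survey asks about bodily pain in general over 4 weeks (Appendix A). Follow-up is at 4-12 weeks (Table 1), so a transient episode can be missed.
3. Increased swelling (likely). It has no AE-log route. Swelling on the NRS, pitting grade (6.8) and circumferences (6.7) are taken at both visits. They show the state on the day, not episodes in between.
4. Cellulitis (less likely). It is named in 6.11.4 and logged in both arms.
5. New or increased trunk or genital edema (less likely). It is not named in 6.11.4. That list is open, so an investigator might enter it, but nothing says so.
6. Electric shock (highly unlikely). This is a device hazard and does not apply to controls.

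The sections on scope do not agree. Section 6.11.2 logs device-related events, and 11.1 makes the investigator aware of serious and device-related events. Section 8.0 has all adverse events reported to the IRB, and 8.3 has them reported as required. The set collected under 6.11 is narrower than the set that 8.0, read literally, would report.

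Illustration of size. The documents give no event rate, so it is assumed.

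- Inputs: n = 15 analyzable subjects per group (section 13.1); the same true rate p in both arms; every Flexitouch Plus event logged; no control event logged.
- Expected logged count in the Flexitouch Plus arm = n × p, against 0 in control.
- p = 10%: 15 × 0.10 = 1.5 against 0.
- p = 20%: 15 × 0.20 = 3.0 against 0.
- p = 30%: 15 × 0.30 = 4.5 against 0.

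Suppose someone ran a two-sided Fisher test on such a table. For x events against 0 its p-value is 2 × C(15,x) / C(30,x). At x = 4 this is 2 × 1365 / 27405 = 0.100, and at x = 5 it is 2 × 3003 / 142506 = 0.042. Five logged events are therefore needed. The binomial chance of five or more among 15 is 1.3% at p = 10%, 16.4% at 20% and 48.5% at 30%.

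These are upper bounds on the artefact in that direction. If some device-arm events were not judged to be associated with the device, fewer would be logged. If none were, the log would read 0 against 0 whatever the true rates.

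**The case against.** The strongest reply is that the study does not plan this comparison. Objectives and endpoints (sections 3.0 and 4.1) concern effectiveness, section 13 specifies no AE table by arm, and the device is cleared and used on label. Logging device-related events only is a coherent choice, repeated in 11.1. All of that stands, and it sets the weight of the point.

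A reader might infer that the control arm records no non-serious events at all. The documents do not support that. The 6.11.4 log covers both arms, whatever the seriousness, and its list is open. Controls may also receive an in-clinic Flexitouch Plus treatment at Follow-up (6.10), so a device-related entry is possible for them, although only after Follow-up data collection is complete.

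A reader might also infer that tolerability cannot be compared in any respect. That goes too far as well. Serious events and complications can be compared, and pain and swelling are measured in every subject. What those measures leave out is skin irritation short of breakdown and episodes that resolve before the visit.

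It is tempting to call the 8.0 commitment impossible to meet. Read with 8.3 and with the reference in 6.11 to reportable events, it can mean all reportable events. This is loose wording that needs reconciling. Likewise, 6.11.2 does not say who decides that an event is associated with the device. That a treating investigator who knows the assignment would do so is a reasonable inference from the open envelope procedure in 6.5, but it is not stated.

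Finally, full recording would not verify equal risk in so small a study: 3 of 15 has an exact 95% interval of roughly 4% to 48%. That is correct. The gain is that recording would no longer depend on arm, which matters even for a descriptive table.

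**Conclusion.** The point holds for the AE log and for the treatment period. On that log, non-serious events are recorded only when associated with Flexitouch Plus, so overall non-serious AE rates cannot be compared between arms and the log cannot inform the 8.1 expectation. Because section 13 plans no AE comparison, this restricts what can be reported on safety and makes no planned analysis wrong.

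The size, up to 1.5 to 4.5 expected logged events against 0, rests on assumed equal true rates of 10% to 30%, complete logging in the device arm and 15 subjects per arm. The asymmetry itself follows from the text and needs no assumed rate. It is a cheap improvement worth making.

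**What to change.** In 6.11.2, record all adverse events, or at minimum every event type listed in 8.1, in both arms on the same AE log at the assessments already in Table 1. Make relatedness to the device and relatedness to compression fields of the record, not conditions for entry. This also gives side effects of graduated compression a study record alongside the commercial reporting in 6.11.5. Add a line to section 13.2 that adverse events will be summarised descriptively by arm. Reconcile 6.11.2, 8.0, 8.3 and 11.1 so that they state one scope for recording and one for IRB reporting.

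The cost is a few more log entries for about 36 women (15 + 3 replacements = 18 per arm, times 2), with no extra visit or staff.

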6.11.3 Adverse Event Severity

Severity will be assessed by the investigator using the following definitions:

- Mild: Subject awareness of sign or symptom, but easily tolerated.
- Moderate: Interferes with normal activities.
- Severe: Incapacitating, with inability to perform normal activities.

6.11.4 Venous-, Lymphedema-, and Lipedema-Related Complications

Information about venous-, lymphedema-, and lipedema-related complications, including cellulitis, lymphangitis, deep vein thrombosis, skin breakdown, lymphorrhea, and lymphangiosarcoma, will be recorded on the Complication & Healthcare Utilization log.

6.11.5 Device Observations

Device observations regarding the Flexitouch Plus will be recorded on a Device Observation log and reported to Tactile Medical to assess the need for complaint reporting. Device observations include device failures, device malfunctions, use errors, and user preferences, as defined below:

- **Device Failure**

A device failure has occurred when the device is used in accordance with the IFU but does not perform as described in the IFU and also negatively impacts treatment of the study subject.

- **Device Malfunction**
A device malfunction occurs when an unexpected change to the device that is contradictory to the IFU is observed, which may or may not affect device performance.
- **Use Error**
A device use error is an act or omission of an act that results in a different medical device response than intended by the manufacturer or expected by the user. Use error includes slips, lapses, and mistakes. An unexpected physiological response of the subject does not itself constitute a use error.
- **Device Issue**
Any other issue with the device that does not fall into one of the above categories.
- **User Preference**
Information on user expectations, likes, dislikes, motivations, and inclinations that drive subject satisfaction with the device.

Any unexpected side effects, product quality problems, use errors, or therapeutic failures related to graduated compression will be reported through the standard commercial means, including: direct communication with manufacturer personnel or online filing by the investigator at MedWatch (<https://www.accessdata.fda.gov/scripts/medwatch/index.cfm>).

7.0 Subject Discontinuation or Exit

7.1 Early Discontinuation

Subject participation may be discontinued prior to study completion for any of the following reasons:

- **Withdrawal of Consent**
Subjects may withdraw their consent to participate at any time. If a subject withdraws consent, previous information that has already been obtained will be available for analysis.
- **Adverse Event**
Subject experiences an adverse event that in the investigator's clinical judgement necessitates discontinuation of their participation in this study.
- **Discretion of the Investigator**
Subjects may be withdrawn at the investigator's discretion in the event of subject noncompliance, changes in the subject's health, or other reasons based on the investigator's clinical judgment.

Subjects withdrawn prior to completing the study will be asked to return to clinic to complete Study Exit procedures.

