2.3.2 Conservative Care

Standard care for patients under the Principal Investigator's care includes 30-40 mmHg graduated compression up to waist, dietary counseling, exercise, and a referral for Complete Decongestive Therapy (CDT). Based on each patient's situation (e.g., insurance coverage, willingness/ability to independently comply with care, time constraints, etc.), some or all of these recommendations are typically followed. In this "real-world" study, no attempt is being made to control what will or won't be used in terms of conservative care since it varies in clinic practice for each patient.

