4.4 Treatment Assignment and Duration

Eligible patients will be randomized (1:1) using sealed envelopes to one of the following treatment cohorts:

- Conservative care alone (may include 30-40 mmHg graduated compression up to waist, dietary counseling, exercise, and/or referral for CDT); or
- Flexitouch Plus with conservative care.

Following randomization, a product demo may take place to confirm the subject is able to tolerate prescribed care.

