6.5 Randomization

If the subject meets all of the inclusion criteria and none of the exclusion criteria, they will be randomly assigned to Flexitouch Plus with conservative care or conservative care alone. Randomization codes will be generated in a permuted block design. The block size will be balanced within each block, and will maintain a 1:1 ratio between the treatment groups.

The randomization code will be distributed by sealed envelope and assigned sequentially as soon as an eligible subject completes the Baseline measurements. The appropriate staff member will obtain the next sequentially sealed randomization envelope and open it while the subject is present.

The randomization assignment cannot be changed or chosen by the subject or the investigator. The randomization envelope, as well as evidence of treatment group assignment, should be placed in the subject's binder.

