6.10 Treatment

Following randomization, collection of measurements, and the completion of questionnaires, patients will be trained on the conservative care prescribed by the investigator (or designee).

Patients randomized to the Flexitouch Plus will obtain a device through standard commercial means (via self-pay, patient assistance, or insurance programs). The standard prescription of ‘Full Leg and Core (L1)’ with daily simultaneous bilateral lower extremity treatment (~60 minutes) at normal pressure levels will be used unless alternate programming is selected by the investigator. Alternate programming (e.g., twice daily, high pressure, additional supplemental lower leg program, etc.) may be used at the investigators discretion if a subject reports inadequate control of lymphedema symptoms prior to the next study visit. While alternate programming is not expected to be necessary, it is important subjects have access to the best care possible at all times in a “real world” study.

Once the prescription is submitted/processed at the Baseline visit, device shipment and training on device use must take place within 60 days or the subject will not be enrolled in the study.

At the Follow-up visit, some or all subjects may receive an in-clinic treatment with Flexitouch Plus after the Follow-up data collection is complete. Additional circumferential (including 4 sites on each leg, 1 site at the hips, and 1 site at the waist using a Gulick II tape measure) and bioimpedance (including whole body ECW/TBW ratio, as well as segmental ratios for the Right/Left Arm, Right/Left Leg, and Trunk) measurements may be collected and recorded immediately after completion of the in-clinic Flexitouch Plus treatment.

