7.2 Study Exit

A Study Exit form will be completed for all subjects to document the reason for discontinuation or the date of study completion. In addition, subjects randomized to conservative care who express an interest in continuing in-home treatment with the Flexitouch Plus outside of the study will receive information from a Tactile Medical representative per standard procedure.

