13.0 Statistical Methods

13.1 Sample Size Determination

The study is not formally powered for a specific primary hypothesis, thus no formal power/sample size estimation was performed. The study sample size was determined based upon a desire to be able to estimate the means of the primary within group endpoints, using 95% confidence intervals, with the estimation of the endpoint means to have a precision (half width of the confidence intervals) of approximately 40% of the observed standard deviation. To achieve these parameters, we have determined a target analyzable sample size of 15 subjects (30 total legs as the observational units) per group. To accommodate an expected attrition rate of up to 20%, a total of 3 subjects per arm will be replaced, if they fail to fully complete the study.

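### Section 7.1 allows withdrawal from the study without criteria in either arm, and the plan does not secure the outcomes of women withdrawn, so data can be lost selectively from the primary within-group analysis

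*Combined protocol and SAP*

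**What the plan says.** Section 7.1 lists reasons for ending a subject's participation in the study. Besides withdrawal of consent and adverse events, a woman may be withdrawn at the investigator's "discretion in the event of subject noncompliance, changes in the subject"; the sentence continues with her health and with any other reason resting on clinical judgement. No threshold or definition is given, and the text is not limited to one arm. It does not distinguish stopping treatment from leaving the study.

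On what follows a withdrawal:

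- Section 7.1: "Subjects withdrawn prior to completing the study will be asked to return to clinic to complete Study Exit procedures".
- Section 7.2: "A Study Exit form will be completed for all subjects to document the reason for discontinuation or the date of study completion". No outcome assessment is named, and Table 1 has no exit column.
- Section 13.1: "a total of 3 subjects per arm will be replaced, if they fail to fully complete the study".
- Section 13.2: summaries use subjects with reported data, nothing is imputed, and missing data will not be reported explicitly. No analysis population is defined.

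On who knows the assignment: "Eligible patients will be randomized (1:1) using sealed envelopes" (section 4.4), and under section 6.5 a staff member takes the next envelope and is to "open it while the subject is present". No blinding is described anywhere.

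On what a woman could fail to comply with: in the device arm, "daily simultaneous bilateral lower extremity treatment (~60 minutes) at normal pressure levels will be used unless alternate programming is selected by the investigator" (section 6.10). For conservative care, section 2.3.2 says that "no attempt is being made to control what will" or will not be used.

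**The concern.** Withdrawal under section 7.1 happens after randomisation, at the discretion of someone who in all likelihood knows the arm, and no rule limits it. If the women withdrawn tend to be those doing less well, the women left in the analysis look better than the group that was randomised. Section 13.2 makes the within-group change from baseline the primary analysis. That analysis has no comparator to cancel such a shift, so it is exposed even when both arms lose women in the same way.

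A link between withdrawal and outcome is possible on the plan's own text. Section 8.1 lists pain or discomfort and increased swelling among the likely treatment risks. Pain and swelling are also among the primary symptom measures (sections 4.1 and 6.9.3), so a change in health could itself be a poor endpoint value.

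The between-arm comparison is at stake if the arms are affected unequally. The device arm carries a defined daily regimen on top of the same loosely specified conservative care, so there is more in that arm to be judged noncompliant with.

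**Working it through.** **The plan's own figures.** Section 13.1 targets 15 analysable women (30 legs) per group, for a 95% confidence interval half-width of about 0.40 SD. With 30 legs treated as independent, 1.960/√30 = 0.358 SD (normal) or 2.045/√30 = 0.373 SD (t), which fits the target. With 15 women as the unit it is 0.506 SD (normal) or 0.554 SD (t); that is a separate matter. Replacing 3 per arm gives 15 + 3 = 18 women per arm, and 3/15 = 20% matches the stated attrition.

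**Path of a withdrawn woman.** She is randomised with the assignment open (6.5), withdrawn without criteria (7.1), asked back for exit procedures described only as a form (7.1, 7.2), and replaced if among the first 3 in her arm (13.1). If no Follow-up values were recorded, she is absent from the results (13.2). No step requires her outcome to be measured or says in which set she is analysed.

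**Illustration 1: withdrawn women have no change.** Assume 18 randomised to the device arm, k of them withdrawn with zero change, and mean change D in the rest.

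- Mean over all randomised: D × (18 − k)/18.
- Mean reported: D.
- Overstatement: 18/(18 − k) − 1.

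| k | Calculation | Overstatement |
|---|---|---|
| 1 | 18/17 − 1 | 5.9% |
| 2 | 18/16 − 1 | 12.5% |
| 3 | 18/15 − 1 | 20.0% |

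If instead 15 + k are randomised so that exactly 15 are analysed, the overstatement is k/15: 6.7%, 13.3% and 20.0%. These percentages apply to the device-arm mean. If no control woman is withdrawn, the between-arm difference shifts by the same absolute amount, D × k/18 (0.056D, 0.111D, 0.167D) in the 18-randomised case.

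**Illustration 2: withdrawal correlated with outcome.** Simulation with 100,000 replicates: 18 women per arm, normal outcomes, no true effect, and 3 women removed on a score that has correlation r with poor outcome. The one-arm column compares 15 filtered with 15 unfiltered women. Error rates are for two-sided tests at 0.05.

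| r | Shift in arm mean | Within-arm type I error | Between-arm, one arm filtered | Between-arm, both filtered alike |
|---|---|---|---|---|
| 0 | 0 SD | 5.1% | 5.0% | 5.1% |
| 0.3 | 0.085 SD | 6.3% | 5.8% | 5.2% |
| 0.5 | 0.14 SD | 9.1% | 7.0% | 5.8% |
| 1 | 0.28 SD | 27.4% | 14.6% | 9.4% |

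With one woman removed, the shift runs from 0 SD (r = 0) to 0.11 SD (r = 1). When both arms are filtered alike, the mean between-arm difference stays at about zero, but each arm's own change remains shifted. Against the 0.40 SD precision target, a shift of 0.14 SD is 35% of the half-width (0.14/0.40). The last row, where the 3 worst outcomes are always the ones removed, is an upper limit and not an expectation.

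The documents give no withdrawal rate by arm or reason and nothing that fixes r or k, so neither table is an estimate.

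**The case against.** The strongest reply is that the clause is a routine investigator-discretion provision in an exploratory, unpowered study whose between-arm comparison is secondary, and that the plan already contains some protection. Withdrawn women are asked back, the reason for discontinuation is recorded, and section 6.10 answers inadequate symptom control with alternate programming, which keeps a woman on treatment. Table 1 has no visit between Baseline and Follow-up and no adherence record, so no routine source would tell the investigator who is under-using the device.

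Much of this stands, and it rules out several stronger readings that a reader might infer:

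- *That only the device arm is filtered.* Section 7.1 covers all subjects. Willingness to follow prescribed care is an entry criterion for everyone (4.2.1), and conservative care is prescribed and trained (6.10). Section 2.3.2 makes noncompliance harder to define in the control arm; it does not make it impossible.
- *That poor responders are removed.* Poor response is not a named ground. The wording on health and other reasons permits such a withdrawal but does not call for it.
- *That the clause contradicts the real-world purpose.* In sections 2.3.2 and 6.10 that phrase concerns uncontrolled conservative care and access to best care. Neither section says incomplete device use is under study.

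The 60-day rule on device shipment and training (6.10 and the Table 1 footnote) is a clearer device-related filter after randomisation, but it is a separate issue.

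The reply does not close the main gap. An exit visit described only as a form does not secure outcomes, and the absence of an adherence measure leaves noncompliance to ad hoc judgement. An exploratory aim built on estimating means still needs those means to describe the women randomised.

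**Conclusion.** The point holds as a gap in the plan. Participation can be ended without criteria in either arm, assignment is open, and nothing ensures that withdrawn women are measured or analysed. The primary within-group change can be biased whether or not the arms differ. Bias between the arms needs unequal withdrawal, which sections 2.3.2 and 6.10 make plausible but do not establish. That the investigator knows the arm is an inference from the open assignment, though a safe one.

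The size is unknown. The 6% to 20% range is a scenario that rests on 18 randomised, 1 to 3 device-arm withdrawals, zero change in those withdrawn and, for the effect on the comparison, no control withdrawals. It would be larger if the withdrawn women worsened, and zero if withdrawal is unrelated to outcome. A reader should not take it as a forecast. This is a cheap improvement, not a defect that invalidates the study.

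**What to change.** Change the wording in four places:

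1. **Section 7.1.** Separate stopping or under-using treatment from ending study participation, and remove noncompliance as a ground for ending participation. State that a woman who stops or under-uses the device or conservative care for any reason, including at the investigator's discretion or under the other-reasons wording, is still asked to attend the scheduled Follow-up unless she withdraws consent or cannot be assessed. Clinical decisions about stopping treatment stay with the investigator and are not affected.
2. **Section 7.2 and Table 1.** Where the scheduled Follow-up will not take place, do the Follow-up assessments at the exit visit and record the date.
3. **Section 13.1.** State that a replacement is additional and does not remove the data of the woman replaced.
4. **Section 13.2.** Define an analysis set in which every woman is analysed in her randomised arm, and report withdrawals by arm and reason.

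The cost is protocol wording, with no visit beyond those already planned or requested; an exit visit would take longer where assessments are added. The device-arm mean change may come out slightly smaller because incomplete users are included.
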